5 STUDY DESIGN

This is a phase 1/2, two-stage, sequential cohort dose escalation study. In phase 1, subjects will be allocated to BID doses of 10 mg/d up to 40mg/d. The starting dose will be 10 mg/d (5mg BID). Each cohort will include up to 6 subjects. Once MTD is reached, 10 additional subjects will be treated during the first stage of phase 2 (stage 1) at the MTD. The tiral will be terminated if 1 or fewer respond. If the trial goes on to the second stage, a total of 29 patients will be studied to determine efficacy in phase 2.

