6.3 Definition of Maximum Tolerated Dose

The maximum tolerated dose (MTD) is defined as the highest dose where < 33% of subjects experience DLT.

Dose Escalation Scheme

In phase 1 of this study, subjects will be allocated to starting doses (10 mg/d to be escalated up to 40mg/d, which is outlined in the table above). The second phase of the study (phase 2) will enroll a maximum of 29 subjects at the MTD determined in phase 1. In each cohort in the phase I study, up to 6 subjects will be enrolled. Based on whether DLTs are observed during 8 weeks of treatment, the dose for the subsequent cohort will be determined. If no DLT is observed during an 8 week period then another 6 subjects will be enrolled at the next dose level (see section 6.2.1 table). If 1 DLT is observed after three subjects are enrolled then dose escalation will continue at the same dose level until 6 total patients are enrolled. If a total 1 of 6 subjects enrolled experience at DLT after all subjects have had an 8 week monitoring period then dose escalation can proceed. If 2 or more of 6 total subjects experience a DLT then dose escalation is complete and the MTD will be the antecedent dose level. Dose escalation will proceed according to the following scheme. Dose-limiting toxicity (DLT) is defined above.

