15.2 Sample Size/Accrual Rate

If dose escalation is completed as planned, no more than 53 subjects are expected to enroll onto this study at a rate of approximately 3 subjects every month. For the Phase 2 study the Simon's optimal two-stage design will be employed to test the null hypothesis that response rate (RR) equals to 10% versus the alternative that RR equals to 30%. If the treatment is actually not effective, there is a 0.05 probability of concluding that it is. If the drug is actually effective, there is a 0.19 probability of concluding that it is not. The probability of early terminating the trial at the end of first stage under the null is 0.74. After testing the treatment dose on 10 patients in the first stage, the trial will be terminated if 1 or fewer desired respond. If the trial goes on to the second stage, a total of 29 patients will be studied. If the total number responding is less than or equal to 5, the drug is rejected. A sample size of 29 from Phase 2 produces a two-sided 95% CI with a width equal to 0.38 (±19) when the sample proportion is 0.50 that is the maximum width for a CI with an given sample sizes.

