15.3 Statistical Analysis Methods

Demographic and clinical variables for the study patients will be summarized using descriptive statistics (mean, standard deviation, median, inter-quartile range, range, and frequency counts and percentages). Safety and efficacy data will be analyzed overall as well as separately for each dose cohort when appropriate.

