15.5 Efficacy Analysis: ITT

This analysis will include all subjects who have received any protocol treatment, regardless of patient eligibility or duration of treatment. Those who have no response assessment data due to reasons such as drop out of the study, withdrawal consent, or lost to follow-up will be treated as non-responders for various response evaluations. The proportion of subjects achieving a complete platelet response will be summarized. A 95% exact binomial confidence interval of the proportion will also be provided for all participants treated at the MTD. In addition, a second analysis of evaluable subjects will be performed. Evaluable subjects are defined as those who complete at least 8 weeks of therapy an complete there first treatment bone marrow biopsy and aspirate to evaluate study drug response.

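### Section 15.5 puts the response confidence interval on everyone treated at the MTD, while 15.2 tests 29 phase 2 patients; the interval also ignores the stage 1 stop, with a smaller effect

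*Combined protocol and SAP*

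**What the plan says.** Section 15.5 plans the efficacy interval in one sentence: "A 95% exact binomial confidence interval of the proportion will also be provided for all participants treated at the MTD". It names no set narrower than that and no adjustment for the interim stop. The sentence before it refers to complete platelet response.

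Section 15.2 describes a different set. The Simon design is run on phase 2 patients: "After testing the treatment dose on 10 patients in the first stage, the trial will be terminated if 1 or fewer desired respond", and at the end "If the total number responding is less than or equal to 5, the drug is rejected". The precision statement is tied to the same patients: "A sample size of 29 from Phase 2 produces a two-sided 95% CI with a width equal to 0.38".

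Section 5 makes these patients new: once the MTD is reached, "10 additional subjects will be treated during the first stage of phase 2". The synopsis agrees, with a maximum accrual of 53 made up of 24 in phase 1 and 29 in phase 2. The phase 1 cohort at the MTD is therefore not among the 29. Its size is given in 6.3: "In each cohort in the phase I study, up to 6 subjects will be enrolled".

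The synopsis, Section 7 and Section 10.2 also let subjects from other phase 1 cohorts move up to the MTD, after week 16 in the synopsis and after week 17 in the other two.

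**The concern.** The go/no-go decision is made on one set of patients and the response estimate may be reported on another. Nothing in the plan says which set is primary, so the choice could be made after the data are seen.

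Two groups enter through the wording of 15.5. The first is the phase 1 cohort at the MTD. The second, if the words are taken literally, is lower-dose subjects who later receive the MTD. Continuation after week 16 is for responders (Section 7), and Section 9.3 requires the drug to stop when there is no clinical benefit by then. Those who move up have therefore been selected for benefit, and counting them would favour response.

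The second issue is the method. An ordinary exact binomial interval treats 10 or 29 as a fixed sample size. Here the size depends on the first 10 results, so the nominal level is not guaranteed.

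**Working it through.** **Inputs.** Null and alternative response rates 10% and 30%; stage 1 of 10 patients, stop at 1 or fewer; 29 in total, drug rejected at 5 or fewer (15.2). Phase 1 cohort at the MTD up to 6 (6.3); the escalation table in 6.3.1 allows 3 to 6. Calculations involving this cohort assume the same true rate in it as in phase 2.

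**1. Reproducing the plan's figures.** With X from Bin(10, p) and Y from Bin(19, p):
- Early stop at p = 0.1: 0.9^10 + 10 × 0.1 × 0.9^9 = 0.736 (plan 0.74).
- Type I error: sum over x = 2 to 10 of P(X = x) × P(Y ≥ 6 − x) at p = 0.1 = 0.0471 (plan 0.05).
- Power: the same sum at p = 0.3 = 0.8051, so beta = 0.195 (plan 0.19).
- Clopper-Pearson width at a proportion of 0.5 with n = 29: 0.690 − 0.310 = 0.380 (plan 0.38).

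The design and the width are both figures for the 29.

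**2. Size of the set as worded.** 29 + 3 to 6 = 32 to 35 after continuation, or 10 + 3 to 6 = 13 to 16 after a stage 1 stop. If the MTD were the top level, up to 24 − 6 = 18 lower-dose subjects could exist, of whom only responders could move up. The documents give no basis for sizing that effect.

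**3. Effect of pooling with 6.** Single-stage 95% intervals against the 10% null:
- 5/29 (drug rejected) plus 3/6 = 8/35: 10.4-40.1%, which excludes 10%. The chance of 5/29 with 3 or more of 6 is 0.09%, 1.0% and 0.8% at true rates of 10%, 20% and 30%.
- 7/29 (drug not rejected) plus 0/6 = 7/35: 8.4-36.9%, which includes 10%. Chance 0.6%, 3.1% and 1.2%.
- 6/29 plus 2/6 = 8/35 goes the other way and brings the interval into line with the rule.

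Total probability that the interval and the rule disagree at those three rates: 2.9%, 12.5% and 6.6% on phase 2 alone (all from 6/29), and 3.4%, 12.9% and 5.8% pooled with 6. With 3 to 5 pooled the ranges are 3.5-3.8%, 13.9-17.3% and 6.2-8.9%.

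**4. Coverage of the single-stage interval on phase 2 patients.** Coverage at p is the sum of the two-stage probabilities of all outcomes (0/10, 1/10, or s/29) whose interval contains p.
- True rates of 10-30%: 97.2-99.3%; the upper limit misses at most 0.55% of the time (nominal 2.5%).
- Below 95% only at true rates of about 31.7-32.5%, 44.6-45.6% and 47.3-48.1%.
- Minimum 94.2% near 45%, with an upper miss of 3.9%. About 2.5 of those points come from 0/10 and 1/10 stops, where the two-stage interval is identical, which leaves about 3.9 − 2.5 = 1.4 points.
- On the pooled set the minimum is 94.4% (3 added) or 94.8% (6 added).

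**5. Two-stage exact interval.** Order the outcomes 0/10, 1/10, 2/29, …, 29/29. The lower limit solves P(outcome at or above observed) = 0.025, and the upper limit solves P(outcome at or below observed) = 0.025. Minimum coverage is 95.0%.

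| Phase 2 result | Single-stage 95% | Two-stage 95% |
|---|---|---|
| 2/29 | 0.8-22.8% | 2.5-44.5% |
| 5/29 | 5.8-35.8% | 6.7-44.8% |
| 6/29 | 8.0-39.7% | 8.6-45.5% |
| 7/29 | 10.3-43.5% | 10.7-46.9% |
| 10/29 | 17.9-54.3% | 18.1-54.8% |

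**6. The smallest success, 6/29.** One-sided p against 10% is 0.064 single-stage and 0.047 two-stage. The 90% lower limit, which matches a one-sided 0.05 test, is 9.4% single-stage and 10.2% two-stage. At 95% both intervals include 10%.

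**The case against.** The set may be deliberate. Section 15.6 describes the study as mainly phase I with an extension at the MTD and centres its summaries on subjects at that dose. Section 15.3 adds: "Safety and efficacy data will be analyzed overall as well as separately for each dose cohort when appropriate". The figure of 29 in 15.2 is a precision statement and does not expressly confine the reported interval to those patients. Pooling with 6 leaves agreement with the rule almost unchanged. All this is fair, and it means pooling is defensible as a supportive summary. It does not say which set carries the primary estimate, nor does it deal with subjects who move up.

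On the method, a reader might infer that the planned upper limit is materially too low around the decision boundary. The calculations do not support that: across the design range of 10-30% the interval is conservative, and the shortfall elsewhere is at most 0.8 points. Stagewise ordering is also one choice among several, and it has a cost. It ranks a 1/10 stop below every 29-patient result, so the upper limits for 2 to 6 of 29 all lie at about 44.5-45.5%. Mean 95% width at true rates of 10-20% rises from about 0.35 to 0.38. The plan contains no 90% interval; that comparison is added here because of the one-sided level in 15.2 ("If the treatment is actually not effective, there is a 0.05 probability of concluding that it is").

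Finally, if 15.5 really means complete platelet response, the coverage figures do not apply, because the stop would be driven by a different endpoint.

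**Conclusion.** The point holds, chiefly as a mismatch of analysis sets. Section 15.5 as worded reports on up to 35 patients, or more if later dose increases count, while 15.2 tests 29. Reversals from pooling with the phase 1 cohort are possible but uncommon. Including subjects who moved up would bias towards response by an amount that cannot be sized from the documents.

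The stopping-rule issue is secondary. The single-stage interval loses its guarantee, but only slightly and only at true rates above about 31%. The main gain from a two-stage interval is consistency with the Simon rule at 6/29, seen at the 90% level.

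Two stronger readings should be set aside. A reader might infer that the go/no-go decision is compromised; it rests on counts in phase 2 patients and is unaffected. A reader might also blame the stopping rule when a 95% interval at 6/29 includes 10%. The two-stage interval includes it too, because the test is one-sided at 0.05 and the interval is two-sided at 95%.

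All figures assume that the proportion in 15.5 is the 15.2 response endpoint. The pooled figures also assume 3 to 6 phase 1 subjects at the MTD with the same true rate as phase 2.

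**What to change.** In 15.5, define the primary response interval on subjects enrolled in phase 2 at the MTD: 10 if the trial stops at stage 1, otherwise 29. State that every subject is analysed by assigned starting dose, so that a later increase to the MTD does not move anyone into the set. Report the pool with the phase 1 MTD cohort as supportive.

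Add a stagewise-ordered two-stage exact interval, alongside or in place of the single-stage one, at 95% and also at 90% to match the one-sided test. Note that the 95% interval at 6/29 still includes 10%, and state the loss of width (2/29 becomes 2.5-44.5% instead of 0.8-22.8%).

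The complete platelet response wording in 15.5 must be reconciled with the 15.2 endpoint, and the week 16 and week 17 passages on moving up must be reconciled with each other.

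The cost is SAP wording and a few lines of code, with no extra patients. Up to 6 phase 1 subjects leave the primary interval but remain visible in the supportive one.

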15.6 Analyses of Secondary Endpoints

Analyses of the following secondary endpoints will be performed as well:

- 15.6.1 Acute myeloid leukemia (AML) transformation according to WHO criteria.
- **15.6.2** Overall survival (OS).
- **15.6.3** Duration of response.
- 15.6.4 The Myeloproliferative Neoplasms Symptom Assessment Form (MPN-SAF) at baseline and at best response.
- 15.6.5 >50% decrease in splenic length as measured by physical exam if applicable
- **15.6.6** The suppression of pSTAT5 intracellular signaling after ruxolitinib in CMML subjects (pretreatment, at 1-2hr post treatment, cycle 2, cycle 4, and progression.)
- **15.6.7** Determine number of colonies formed in the presence of GM-CSF and/or ruxolitinib (pretreatment and progression) as a future predictor of response.
- **15.6.8** Mutational status in our CMML subjects by sanger sequencing of JAK2, c-CBL, N-RAS, K-RAS,RUNX-1, TET2, SRSF2, EZH2, ASXL1, and DNMT3a (pretreatment and progression).
- **15.6.9** Mutational status of JAK2 tyrosine kinase at time of progression by deep sequencing of JAK2 to include M929I, Y931C, G935R, R938L, I960V, E985K.

(pretreatment and at progression)

We recognize that this is mainly a phase I study with an extension phase at the MTD. However, preliminary data on the above endpoints will prove to be very useful for further investigation of this protocol's treatment. Such data will be summarized appropriately focusing mostly on the subjects treated at the MTD dose in an exploratory fashion. Both point estimates and 95% confidence intervals will be reported, if feasible. Time-to-event endpoints such as OS will be summarized using the Kaplan-Meier product-limit method.

16 Laboratory Correlates

Unless otherwise specified, all laboratory correlates will be performed in the laboratory of [name] under the direction of Drs [name] and [name].

H.LEE MOFFITT CANCER CENTER

CC: [name]

STABILE RESEARCH BUILDING

SRB-2

[name]

16.1 Sample Collection

At Screening and weeks 1, 5, 9,13, and 17 (see study calendar), peripheral blood will be collected. Designated study personnel will collect the sample from the laboratory draw area. Peripheral blood will be collected in six green top (heparinized) 10cc tubes and one red top (clot activator or no additive) 10cc tube for a total of seven tubes and 70cc of peripheral blood. At the time of the first dose, peripheral blood will be collected twice: once at the time of the first dose (or up to one hour prior to the first dose) in six green top 10 cc tubes and one red top 10 cc tube, and again three hours after the first dose (+/- 30 minutes) in six green top 10 cc tubes and one red top 10 cc tube, for a total of 14 tubes and 140cc of peripheral blood. At Screening and weeks 8 and 16 (see study calendar), bone marrow aspirate will be collected in three lavender (EDTA) 10cc tubes for a total of 30cc. These will be shipped to the H. Lee Moffitt Cancer Center laboratory as directed above within 24hrs and will be processed first by centrifugation (730 rcf for 5 minutes) to collect the supernatant (plasma from green top or lavender top;

serum from red top). Green top and lavender top samples will be additionally processed by centrifugation (530 rcf for 20 minutes) with density gradient medium to collect the mononuclear cellular layer, followed by the addition of RBC lysis buffer to remove RBCs and debris. The mononuclear cells will be cryopreserved as previously described and stored in liquid nitrogen for later use labeled with a unique identifier that corresponds to each patient known only to the investigator and study personnel. The plasma and serum will be cryopreserved for later use labeled with a unique identifier that corresponds to each patient known only to the investigator and study personnel.

16.2 pSTAT5 as a pharmacodynamic marker for ruxolitinib.

At the time of the first dose the subjects' (may be up to one hour prior to first dose) peripheral blood will be collected, processed and stored as above. Peripheral blood will again be drawn three hours after the first dose (+/- 30 minutes) and be collected, processed and stored as above. Peripheral blood will also be collected at the assigned time points (see study calendar) and processed as above. These samples will be batched for analysis after 10 samples have been processed and cryopreserved. They will be reconstituted in STEM span and 20% FBS in the laboratory of [name]. pSTAT5 will be measured using phos-flow cytometry as previously described at baseline, after one hour of serum free condition, and then stimulated with 0.1, 1, and 10 ng/ml of GM-CSF. The in vitro efficacy of ruxolitinib will also be evaluated by the addition of increasing doses of ruxolitinib and measurement pSTAT5 as above.

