3 STUDY ENDPOINTS

3.1 Primary

- 3.1.1 The maximum tolerated dose (MTD) of ruxolitinib for the treatment of CMML. The MTD is defined as the highest dose where less than 33% of subjects experience a drug related predefined dose limited toxicity (DLT).
- 3.1.2 Proportion of subject achieving clinical benefit defined as hematologic improvement, complete remission, partial remission, or stable disease by the IWG 2006 criteria (see appendix B)

- 3.2 Secondary
- **3.2.1** Acute myeloid leukemia (AML) transformation according to WHO criteria.
- **3.2.2** Overall survival (OS).
- **3.2.3** Duration of response.
- 3.2.4 The Myeloproliferative Neoplasms Symptom Assessment Form (MPN-SAF) at baseline and at best response.
- 3.2.5 >50% decrease in splenic length as measured by physical exam if applicable
- **3.2.6** The suppression of pSTAT5 intracellular signaling after ruxolitinib in CMML subjects (pretreatment, at 1-2hr post treatment, cycle 2, cycle 4, and progression.)
- **3.2.7** Determine number of colonies formed in the presence of GM-CSF and/or ruxolitinib (pretreatment and progression) as a future predictor of response.
- 3.2.8 Mutational status in our CMML subjects by sanger sequencing of JAK2, c-CBL, N-RAS, K-RAS,RUNX-1, TET2, SRSF2, EZH2, ASXL1, and DNMT3a (pretreatment and progression).
- 3.2.9 Mutational status of JAK2 tyrosine kinase at time of progression by deep sequencing of JAK2 to include M929I, Y931C, G935R, R938L, I960V, E985K. (pretreatment and at progression)

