 - Clinical chemistries including BUN/urea, creatinine, sodium, potassium,
 alkaline phosphatase, alanine aminotransferase (ALT), aspartateaminotransferase
 (AST), , total bilirubin, bicarbonate, calcium, chloride, glucose, LDH, total protein,
 albumin.
 - Urine or serum pregnancy test for females of childbearing potential will be performed at Screening or on Day 1, prior to first dose of study medication.
 Symptom Score using the The Myeloproliferative Neoplasms Symptom Assessment
 - Form (MPN-SAF). (see Appendix D)

Review and record any blood and blood supportive care products for the prior 8 weeks.

- 13.2 Treatment Period (weeks 1-16): Ruxolitinib will be administered as a twice daily oral dose for a 4-week treatment cycle. Subjects will have a CBC with leukocyte differential performed weekly; a blood chemistry will be performed weekly for first cycle and then q 2 weeks. A BM aspirate and biopsy with cytogenetic analysis will be performed after cycle 2 and 4 (weeks 8, 16) to assess pathologic response, cytogenetic response and disease progression. For subjects who achieve CR, marrow CR, or PR a confirmation bone marrow aspirate and biopsy should be obtained 4 to 8 weeks after documentation of CR, marrow CR, or PR.
- 13.3 Week 16 End of Treatment: Subjects will complete a response assessment within one week after their last administration of ruxolitinib. Subjects discontinuing study early should complete their end of treatment visit within two weeks after their last dose of investigational product. Physical exam, vital signs, concomitant medication, adverse event reporting, CBC, and blood chemistry and BM aspirate and biopsy with cytogenetic analysis will be performed.
- Continuation Phase: After completing cycle 4 response assessments, responders may continue to receive ruxolitinib and the final week 16 dose in the absence of DLT or disease progression until marketing approval of ruxolitinib for CMML. Bone marrow biopsy and aspirate will be repeated after every 4 cycles (For subjects who achieve CR, marrow CR, or PR a confirmation bone marrow aspirate and biopsy should be obtained 4 to 8 weeks after documentation of CR, marrow CR, or PR). A CBC will be obtained and complete metabolic profile as per standard of care. The off treatment assessment should be done within a week off treatment.
- 13.5 Off Treatment assessment: includes best response achieved, date of first response, date of loss of response, reason for discontinuation.

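### The pSTAT5, colony, mutation and JAK2 endpoints need a sample at progression, but no research collection is scheduled at progression or after week 17, so that sample is not assured.

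*Combined protocol and SAP*

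**What the plan says.** Section 3.2, repeated in 15.6, sets four laboratory endpoints with a progression time point: pSTAT5 suppression (3.2.6), colony formation (3.2.7), the mutation panel (3.2.8) and JAK2 sequencing (3.2.9). The colony endpoint reads "Determine number of colonies formed in the presence of GM-CSF and/or ruxolitinib (pretreatment and progression) as a future predictor of response". The JAK2 endpoint reads "Mutational status of JAK2 tyrosine kinase at time of progression by deep sequencing of JAK2 to include M929I". Section 16.5 presents the latter as a search for ruxolitinib resistance and says that pretreatment and progression samples will be used.

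Section 16.1 fixes the research collections. For marrow: "At Screening and weeks 8 and 16 (see study calendar), bone marrow aspirate will be collected". For blood: "At Screening and weeks 1, 5, 9,13, and 17 (see study calendar), peripheral blood will be collected". The calendar agrees: the marrow row is marked at pre-study, week 8 and week 16, and the laboratory-correlates row ends at week 17.

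Marrow procedures continue after week 16. For responders in continuation, section 13.4 says "Bone marrow biopsy and aspirate will be repeated after every 4 cycles". For the end-of-treatment visit, in a paragraph that also covers early discontinuation, section 13.3 says "BM aspirate and biopsy with cytogenetic analysis will be performed". Neither mentions research tubes. Calendar footnote d, on the marrow row, adds an aspirate with a goal of 30cc and names no visits.

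The timing also varies. Objective 1.2.9 and section 16.4 accept end of study as an alternative to progression; endpoints 3.2.7 to 3.2.9 and section 16.5 do not.

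**The concern.** The endpoints name a time point that the collection schedule does not contain. Subjects who respond, stay on ruxolitinib and later progress are those in whom acquired resistance would be expected to appear. They pass out of the research schedule at week 17. Staff who follow 16.1 and the calendar literally would take no research material from them at progression.

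At stake is whether objective 1.2.9, and the pretreatment-to-progression comparison in the other endpoints, will have data from the subjects who matter most for it. Cells that are not frozen at the time cannot be recovered later.

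**Working it through.** The documents give no planned number of progression samples, so there is no figure to reproduce. The check sets the required timing against the scheduled collection.

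| Endpoint | Timing required | Tissue | Research collection in 16.1 |
|---|---|---|---|
| 3.2.6 pSTAT5 | several, including progression | blood (16.2) | screening, weeks 1, 5, 9, 13, 17 |
| 3.2.7 colonies | pretreatment and progression | frozen marrow cells (16.3) | screening, weeks 8, 16 |
| 3.2.8 mutation panel | pretreatment and progression; 16.4 also allows end of study | cryopreserved marrow (16.4) | screening, weeks 8, 16 |
| 3.2.9 JAK2 | pretreatment and progression; objective 1.2.9 also allows end of study | not named (16.5) | either list above |

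**Spacing.** On treatment, research marrows are 16 − 8 = 8 weeks apart and research blood draws 5 − 1 = 4 weeks apart. In continuation, marrows come every 4 cycles of 4 weeks (13.2), so 4 × 4 = 16 weeks apart, and no research tubes are named for them.

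**Who is covered.**

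1. *Subjects who stop at week 16.* The week-16 marrow and week-17 blood serve as end-of-study samples where that timing is accepted.
2. *Subjects who progress before week 16, between marrows.* Progression ends treatment (sections 7.6 and 9.3), and 13.3 places an end-of-treatment visit with a marrow within two weeks of the last dose. Section 16.1 does not list that visit. The 14-day marrow window in section 13 lets some of these progressions coincide with the week-8 or week-16 research marrow, but not all. The preceding scheduled blood draw is at most about 4 weeks earlier, visit windows aside.
3. *Subjects who progress during continuation.* No research marrow or blood is named. A 4-cycle marrow may fall well before progression. Whether a marrow is done on stopping is unclear, because 13.3 is headed as the week-16 visit and the off-treatment assessment in 13.5 lists none.

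**How large group 3 might be.** The documents give no time-to-progression distribution. As an illustration only, assume it is exponential with no dropout. With median m in weeks (months × 52/12), the share of progressions after week t is 0.5^(t/m).

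| Assumed median | m (weeks) | After week 16 | After week 18 (14-day window) |
|---|---|---|---|
| 3 months | 13 | 0.5^(16/13) = 43% | 38% |
| 6 months | 26 | 0.5^(16/26) = 65% | 62% |
| 9 months | 39 | 0.5^(16/39) = 75% | 73% |
| 12 months | 52 | 0.5^(16/52) = 81% | 79% |

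The illustration ignores the week-16 stop for subjects without benefit, so it shows only that the group need not be small. It does not estimate its size.

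**The case against.** The strongest reply is that the plan does intend progression samples and has procedures that could supply them. Section 16.5 says they will be used. Marrows continue every 4 cycles and at the end-of-treatment visit. Footnote d attaches a 30cc aspirate to the marrow row without limiting it to named visits. The calendar also leaves its weeks 18 to 48 marrow cell blank although 13.4 requires marrows then, so a blank cell does not prove that nothing is collected. Objective 1.2.9 and section 16.4 accept an end-of-study sample, and the secondary objectives are declared exploratory.

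Most of this stands, and it rules out stronger readings. A reader might infer that the resistance question cannot be answered, or that no later progressor will contribute data. Neither follows: if footnote d is applied to continuation and end-of-treatment marrows, some will have samples. A reader might also infer that a week-16 sample from a responding subject would be analysed as a progression sample. No section says so; the end-of-study alternative leaves room for mislabelling but does not plan it.

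What the reply does not do is put the collection into the schedule. Footnote d annotates a row marked at three visits, and 16.1 names the same three. Stating that samples will be used in 16.5 does not arrange for them to be taken. The end-of-study alternative supplies no tubes for someone who stops during continuation.

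**Conclusion.** The point holds as a gap in scheduling. Four secondary endpoints need material at progression, while 16.1 and the calendar schedule no research marrow after week 16 and no research blood after week 17. A progression sample is therefore not assured for subjects who progress in continuation or between scheduled marrows. For pSTAT5 the shortfall is mainly after week 17; for the marrow-based assays it also affects early progressors.

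The affected share cannot be derived from the documents, and the 43% to 81% range rests wholly on the exponential assumption. The conclusion takes 16.1 as the controlling list; if the sponsor confirms that footnote d already covers later marrows, the marrow gap narrows to a wording matter, but the blood gap remains. The importance is modest: the endpoints are exploratory, and neither the primary endpoints nor the two-stage decision rule depends on them.

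**What to change.** Amend 16.1 and the calendar as follows.

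- Take the research aspirate and blood tubes at progression or end of treatment as well, using the marrow already performed at the end-of-treatment or early-discontinuation visit (13.3) or the nearest 4-cycle continuation marrow (13.4).
- Where no marrow is done, take research blood alone. Section 16.5 names no tissue for the JAK2 assay, and blood also serves pSTAT5. Blood would not replace the marrow on which 16.3 and 16.4 rely.
- Label each sample by whether progression had occurred when it was taken.
- State that footnote d covers these marrows.
- Use one timing phrase throughout: endpoints 3.2.7 to 3.2.9 and section 16.5 say progression, while 1.2.9 and 16.4 also allow end of study.

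The cost is wording, storage and sample volume at existing visits. At the 16.1 volumes that is 30cc of marrow and 70cc of blood per full collection. Tying the collection to progression or end of treatment, instead of every continuation marrow, limits that burden, though the nearest 4-cycle marrow can be identified only once progression is known or suspected. The sponsor should say how such a marrow will be chosen.
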